Statistical analysis plan (SAP) sections and items described by Gamble et al. (2), concerning Recommended items to Address in a Clinical Trial SAP. Previous version of SAP has been published on Clinicaltrials.gov on January 7th, 2020. Current SAP revisions has been performed due to trial deviations related with COVID-19 and due to insufficient reporting of SAP details in the previously published issue. Trial data collection has currently not been completed and randomized allocation is still concealed (Sep 2020).

Roles and responsibility:

Chief investigator/clinical lead and person writing the SAP

[name] fellow

Orthopedic research unit, Department of Orthopedics and Traumatology, Odense University Hospital, Denmark and

Department of Clinical Research, University of Southern Denmark

Department of Orthopedics, Lillebaelt Hospital, Kolding and Vejle, Denmark

SAP contributor and Senior Researcher

[name]. Associate professor, PhD.

Orthopedic research unit, Department of Orthopedics and Traumatology, Odense University Hospital, Denmark and

Department of Clinical Research, University of Southern Denmark

Signatures:

[name]

[name]

Section 2: Introduction

Background and rationale

Anterior cruciate ligament (ACL) reconstruction is a common arthroscopic procedure, with approximately 300,000 reconstructions performed annually in the United States (3). ACL reconstruction aims to restore functional stability of the knee and can be performed using a variety of different surgical techniques and graft sites (4). The hamstring tendon is one of the most used graft donor sites for ACL reconstruction (3, 5). Although current ACL reconstruction procedures intend to restore internal knee biomechanics, function of the ACL-reconstructed knee remains different from that of healthy knees (5, 6) and is associated with early development of osteoarthritis (7-9). Therefore, information about factors associated with increased risk of osteoarthritis, such as lower-limb muscle strength deficits, should be part of the risk management with ACL reconstruction (7).

Post-surgery, ACLR with the HS graft present a risk that concerns reduced hamstring muscle strength and persistent muscular deficiency has been seen for more than one and two years after reconstruction (10, 11). Moreover, recent studies showed that only 42% of recreational athletes return to pre-injury level of sport activity (RTS) following ACLR (11) and up to 50% of patients develop knee osteoarthritis within 10 years of ACLR (12).

Therefore, regaining adequate strength of the quadriceps and hamstrings muscles after ACLR is considered important. But according to international standards and consensus, ACL postoperative rehabilitation is generally limited to the first 9–12 months post-surgery and the effect on muscle strength deficits after early (first 12 months post-surgery) rehabilitation phase has previously been studied (13, 14). To date, no high level evidence exist to support interventions that can eliminate long-term and persistent risks factors of reduced muscle strength, after HS graft ACLR. Thus, long-term rehabilitation protocols of ACL-reconstructed patients, examining interventions to resolve these muscle strength deficits, especially when using hamstring auto-grafts, are strongly advised (15).

Objectives

The objective of this study is to investigate the effect of targeted exercise on knee- muscle strength and joint function in ACL-reconstructed patients with persistent hamstring muscle deficiency 12–24 months post-surgery compared with low-intensity home-based exercise.

Section 3: Study Methods

Trial design

The study is designed as a prospective, superiority, parallel group randomized controlled trial (RCT) with balanced and blinded randomization (1:1) and blinded outcome assessment (level of evidence: II). The trial adheres to the CONSORT Statement (Consolidated Standards of Reporting Trials) <http://www.consort-statement.org/>.

Trial registration: NCT02939677

Randomization

The randomization sequence was computer generated using Stata 13.0 (Stata Corp, College Station, TX, USA) statistical software with a 1:1 allocation ratio using sequentially numbered opaque, sealed envelopes. The allocation sequence and preparation of the concealed envelopes was completed by a central study coordinator not involved in the conduct of the trial. The primary investigator was blinded to allocation and did not participate in testing, randomization, or completion of intervention. The statistical analysis will be performed on allocation codes only and thus the data analysts will be blinded in relation to intervention allocation. Blinding to treatment allocation of participants, and healthcare providers was not possible due to the nature of the interventions.

Sample size

Sample size estimation was performed using maximal unilateral isometric knee-flexor strength of the operated leg (primary outcome) from a previously published pilot study on the present test protocol and reliability data from our laboratory (6). The statistical model contains one baseline and one follow-up assessment. Between-group difference in change score of 0.31 Nm bw⁻¹ in knee-flexor strength in the ACL-reconstructed limb resulting in a less than 2.5% deficit of the healthy leg prior to intervention was considered of clinical relevance (6). To achieve a statistical power of 80% ($\beta=0.80$), using a SD of 0.37 Nm bw⁻¹ pre and post intervention, and allowing the detection of statistically significant differences at an $\alpha = 0.05$ level (two-tailed testing), a sample size of $n = 23$ was calculated for each group; the estimated recruitment of 50 participants (in total) allows for possible dropouts.

Framework

The study was designed as a prospective, superiority, parallel group randomized controlled trial (RCT) with balanced and blinded randomization (1:1). To minimize interpretation bias, we have a-priori decided how to interpret potential different result scenarios: (1) If knee-flexor strength improvement is superior (statistically significant and clinically relevant (≥ 0.31 Nm bw⁻¹ in knee-flexor strength)) in SNG compared with CON, the combined intervention of strength and neuromuscular exercises will be considered the preferred treatment of choice; (2) If gains in knee-flexor strength are superior in CON compared with SNG, home-based exercises will be considered the preferred treatment of choice; and (3) if knee-flexor strength improvement does not differ between the two treatment groups, the intervention associated with the greatest functional improvement and pain relief, and the least adverse events, will be favored.

Statistical interim analysis and stopping guidance

No interim analyses or planned adjustment of the significance level due to interim analysis, were carried out in this study. Allocation was not disclosed to other study personnel including other site personnel, monitors, corporate sponsors, or project office staff. The primary investigator will maintain blinded as far as possible.

Statistical Analysis plan

Timing of outcome assessments

Assessments were performed at baseline (prior to randomization), following the intervention (12 weeks post baseline) (the primary endpoint) and six months post intervention in accordance with previous protocol paper (1) (Fig. 2; Table 2: Outcome measurements)(1). Six months post intervention data will not be included in the current analyses.

Section 4: Statistical Principles

Confidence intervals and P values

The significance level (α) for statistically significant differences was set at an $\alpha = 0.05$ level (two-tailed testing).

All statistical tests will use an α -level of 0.05 and data will be presented as means and 95% confidence interval unless otherwise stated. No adjustments for multiplicity are planned.

Adherence and protocol deviations

Minor trial deviations from the initial trial protocol (1) and clinical trial registration (NCT02939677) occurred primarily due to the ongoing COVID-19 virus and related shut-down of clinical testing and exercise intervention.

Participants had the possibility to withdraw from the study for any reason at any time. The primary investigator could also withdraw participants from the study to protect their safety and/or if they were unwilling or unable to comply with required study procedures. Throughout the intervention and follow-up period, participants were reminded, by email, about consecutive clinical visits. All withdrawals concerning study participation, will be reported in future publications, including incomplete outcome datasets, due to incomplete follow-up, participant discontinue or deviation from intervention.

Timing, Level, and reason of withdrawal from intervention will be presented in detail in the manuscript's results section and in the flowchart. Lost to follow-up data, reasons, and details of how lost to follow-up data will be presented in both in the manuscript and flowchart.

Statistical Analysis plan

Baseline participant characteristics

List of baseline characteristics is outlined in Figure 1.

Section 6: Analysis

Outcome definitions

Assessments will be performed at baseline (prior to randomization), following the intervention (12 weeks post baseline) (the primary endpoint) and at 6 months follow-up (not reported in current SAP and primary analysis).

Primary outcome includes:

- Between-group change in maximal unilateral isometric knee-flexor strength (hamstring) recorded in the leg that has been operated on, using stabilized dynamometry at a 90° angle (0° = full anatomical extension) (Nm/kg).

Secondary outcomes include:

- Between-group changes in maximal unilateral isometric extensor strength (quadriceps) and hamstring-to quadricep muscle-strength ratio, using the same type of stabilized dynamometry as used for the primary outcome variable (Nm/kg).

Subscale scores (Pain, Symptoms, ADL, Sport & Recreation, and QoL) on the Knee injury and Osteoarthritis Outcome Score (KOOS)

Analysis methods

All outcome measures will be checked for Gaussian distribution by use of QQ-plots and parametric statistical and/or non-parametric analyses will be used when deemed appropriate. All statistical tests will use an α -level of 0.05 and data will be presented as means and 95% confidence interval unless otherwise stated.

Between-group mean differences in outcome measures and 95% confidence intervals will be evaluated using a mixed effect model regression analysis, for analyzing within- and between-subjects variance, both fixed and random variables.

Missing data

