Time since ACLR (months)		
Meniscus injury		
Injured leg		
Time since ACLR (months)		
Primary outcome:		
Maximal isometric knee flexor strength (Nm/kg)		
Secondary outcome:		
KOOS-5 subscales score		
- Pain		
- Symptoms		
- ADL		
- Sport/Rec		
- QOL		
Maximal isometric knee-extensor strength (Nm/kg)		
Hamstring-to-quadriceps ratio		
Not pre-specified explorative outcomes:		
LSI (%)		

Data are shown as mean (SD +/-), except male: female ratio shown as n (percentage). KOOS ranging from 0 to 100 with higher score equal fewer problems. LSI: Limb symmetry index in percent.

Figure 1: Flow diagram

CONSORT 2010 Flow Diagram

Statistical Analysis plan

Table 2: Mean difference within groups and difference between groups at 12 weeks follow up [95% CI].

	SNG (mean [95 CI]) (change Within- group change from baseline)	CON (mean [95 CI]) (change Within- group change from baseline)	Between-group difference from baseline (mean [95% CI])	Effect size between groups (Hedge's g)
Primary outcome				
Maximal isometric knee flexor strength				
Secondary outcome				
KOOS-5 subscales score				

 - Pain - Symptoms - ADL - Sport/Rec - QOL 				
Maximal isometric knee extensor strength				
Hamstring-to-quadriceps ratio				
Not pre-specified explorative outcomes				
LSI				

Figure 2: The between-group changes for primary, secondary, and not pre-specified explorative outcomes. Values are presented as between group difference from baseline and 95% CIs (mean [95% CI]).

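### Does the freedom to use parametric and/or non-parametric analyses leave the deciding analysis of knee-flexor strength open?

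*SAP*

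**What the plan says.** Section 6, Analysis methods, has two statements that are not linked. The first says outcome measures will be "checked for Gaussian distribution by use of QQ-plots and parametric statistical and/or non-parametric analyses will be used when deemed appropriate". The second says: "Between-group mean differences in outcome measures and 95% confidence intervals will be evaluated using a mixed effect model regression analysis".

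Section 3, Framework, fixes in advance how the result will be read. Scenario (1) needs a knee-flexor benefit of the combined training (SNG) that is "statistically significant and clinically relevant", with 0.31 Nm/kg as the relevance limit. Scenario (2) reads: "If gains in knee-flexor strength are superior in CON compared with SNG, home-based exercises will be considered the preferred treatment of choice". Scenario (3) covers no difference between the groups. None of the three names the analysis that supplies the significance verdict.

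The sample size rests on a "Between-group difference in change score of 0.31 Nm" per unit of body weight. The Table 2 shell has a column headed "Between-group difference from baseline (mean [95% CI", beside within-group change and Hedges' g. On blinding, Section 3, Randomization, says: "The statistical analysis will be performed on allocation codes only".

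**The concern.** The first statement covers the primary outcome. It gives no criterion for departing from a parametric analysis and names no test to use instead, and its wording permits both kinds of analysis at once. A mean-based and a rank-based test can disagree on significance in the same data. The scenarios turn on significance, so an analyst holding both p-values could in principle choose the convenient one. Coded groups would not prevent that, because two p-values can be compared without knowing which arm is which.

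At stake would be a type I error above the stated 0.05 and a treatment recommendation that depends on an unrecorded choice.

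There are two lesser worries. A mixed model's normality assumption concerns its residuals and random effects, whereas the plan checks the outcomes. And the usual estimate accompanying a rank test (the Hodges-Lehmann shift) is not the mean difference to which 0.31 refers.

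**Working it through.** **1. What the plan points to.** The places that define the primary result agree:

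| Place in SAP | Scale or method |
|---|---|
| Section 6, Analysis methods, second statement | mean difference and 95% CI from the mixed model, no condition attached |
| Section 3, Sample size | difference in change score, 0.31, SD 0.37 |
| Section 3, Framework, scenario (1) | threshold 0.31 |
| Table 2 and Figure 2 | mean difference [95% CI]; no p-value, median or rank column |

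Nothing in the plan calls for a rank estimate or a rank p-value for the primary outcome.

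**2. The plan's own figure.** Inputs from Section 3, Sample size: difference 0.31, SD 0.37, two-sided alpha 0.05, power 80%.

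n per arm = 2 × (1.960 + 0.842)² × (0.37/0.31)² = 2 × 7.85 × 1.425 = 22.4, so 23, as stated. Power at 23 is 81.1% by the normal formula and 79.4% by the t-test.

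This uses 0.37 as the SD of change. With 0.37 at both visits, that holds at a pre-post correlation of 0.5: 0.37 × √(2 × (1 − 0.5)) = 0.37.

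**3. Type I error.** Simulation with 23 per arm, SD of change 0.37, complete data and no true difference; 40,000 trials per setting (20,000 for the distribution-check row). The t-test on change stands in for the mixed model. In six simulated complete data sets, the random-intercept group-by-time coefficient and its standard error matched the t-test's to four decimals. The normal and lognormal shapes are assumptions.

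| Rule | Normal | Lognormal (sigma 0.5) |
|---|---|---|
| t-test only | 4.9% | 4.8% |
| Mann-Whitney only | 4.7% | 4.6% |
| Test chosen by a normality check (Shapiro-Wilk as proxy for the QQ-plot) | 5.1% | 5.2% |
| Smaller of the two p-values | 5.7% | 6.3% |

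Repeat runs of the last row, some with heavier skew or tails, gave 5.8% to 6.5%. The mean-based test holds its level even with the skewed data, so checking outcomes rather than residuals does little harm here.

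**4. Scenario (1).** Standard error of the difference = 0.37 × √(2/23) = 0.109. Significance at 44 degrees of freedom needs 2.015 × 0.109 = 0.22. The 0.31 threshold lies at 0.31/0.109 = 2.84 standard errors, well beyond that limit, so the threshold rather than the choice of test governs. With no true effect, a false scenario (1) occurs in 0.22% of trials with the t-test and 0.22% with the smaller p-value (lognormal: 0.24% and 0.25%). At a true 0.31 with normal data, scenario (1) is reached in about 50% of trials whichever test supplies significance; the two rates differ by 0.1 percentage points.

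**5. Scenario (2).** If *superior* carries the definition given in scenario (1), a false scenario (2) stays at 0.20% under either rule (lognormal: 0.26% and 0.27%). If it means significance alone, the rate goes from 2.5% to 2.8% (lognormal: 2.4% to 3.2%), and only when the test is chosen by p-value.

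**6. Disagreement between tests.** At a true 0.31 the two tests differ on significance in 5.7% of trials (lognormal 12.0%), and at a true 0.20 in 7.1% (lognormal 16.0%). Step 4 shows that at 0.31 with normal data these hardly touch scenario (1). They bear mainly on whether the groups are said to differ at all.

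**7. A larger figure that does not belong here.** Choosing between a baseline-adjusted model and Mann-Whitney on unadjusted change gives 7.4%, 6.8% and 6.3% at pre-post correlations of 0.5, 0.7 and 0.9. Replacing Mann-Whitney with a t-test on change, so that no rank test is involved, gives 7.3%, 6.8% and 5.9%. Nearly all of that excess comes from baseline adjustment, which the sentence in question does not concern.

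**The case for a change.** The strongest reply is that the deciding analysis is core SAP content. This SAP was revised partly because the previous one gave too little detail, and the scenarios were fixed in advance precisely to limit bias in interpretation. A sentence that leaves the test to judgement sits badly with that aim. One line giving the mixed model precedence would have been cheap, and it could still have been added blind, since data collection was incomplete and allocation concealed at the date of the SAP.

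All of this is fair as comment on the drafting, and the sentence is loose. But it does not show two competing primary analyses. It shows one named analysis and a general remark about distribution checks, which has an obvious use for the KOOS subscales, bounded at 0 and 100. The disagreement rates of 12% to 16% need a markedly skewed change score, and the SAP gives no sign of one for a follow-up-minus-baseline strength difference. The type I error excess needs selection by p-value. The plan describes a QQ-plot check, which leaves the level close to nominal. Coded allocation does not rule out such selection, but it removes most of the means of steering it towards a preferred arm.

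**Conclusion.** No change is called for. Followed sensibly, the plan reports the mixed-model mean difference with its 95% CI and reads scenarios (1) to (3) from it; any non-parametric result is supplementary. Writing that precedence down would only record what the named method, the sample size, the threshold and the results table already imply.

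A distribution-based choice of test leaves type I error at about 5%. Choice by p-value would raise it to about 6.0% (normal) or 6.4% (lognormal). Scenario (1) is unaffected, and scenario (2) is affected only if *superior* there drops the 0.31 threshold. These figures assume 23 per arm, an SD of change of 0.37, complete data and a t-test on change as proxy for the mixed model; multiple imputation was not simulated.

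### The primary mixed model does not say how baseline strength is handled; the plan reads as a raw difference in change, which is valid but usually less precise than a baseline-adjusted analysis

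*SAP*

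**What the plan says.** Section 6, Analysis methods, gives the primary analysis one sentence: "Between-group mean differences in outcome measures and 95% confidence intervals will be evaluated using a mixed effect model regression analysis", followed by "for analyzing within- and between-subjects variance, both fixed and random variables". It names no fixed effect, random effect, covariance structure or baseline term.

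Other parts of the SAP describe the quantity of interest as a change:

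- Section 6, Outcome definitions: "Between-group change in maximal unilateral isometric knee-flexor strength (hamstring) recorded in the leg that has been operated on".
- Section 3, Sample size: "Between-group difference in change score of 0.31" (Nm per kg body weight), and "The statistical model contains one baseline and one follow-up assessment".
- Table 2: within-group changes, then a between-group difference from baseline as a mean with 95% CI.

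The Framework section compares the result with 0.31 Nm/kg and also requires statistical significance. Timing of outcome assessments places the baseline test before randomisation and leaves the six-month data out of this analysis. Analysis methods also provides for a QQ-plot check of the outcomes, after which "parametric statistical and/or non-parametric analyses will be used when deemed appropriate".

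**The concern.** A SAP exists largely to fix the primary model, and this one leaves open a choice that affects the primary interval. A group-by-time contrast, an ANCOVA and a mixed model with a common baseline mean would all comply with the text, and they give different standard errors.

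The natural reading is the group-by-time contrast. With two visits and complete data, including each data set completed by the planned multiple imputation, that contrast equals the raw difference in mean change. It makes less use of the baseline value than an adjusted analysis does.

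At stake is the width of the one interval that is read against 0.31 Nm/kg, in a trial planned at 23 per arm. A lesser matter is that the non-parametric option has no criterion and no named test, and a rank test does not return a mean difference in Nm/kg.

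**Working it through.** **Inputs from the SAP.** Difference 0.31; SD 0.37, given for "pre and post intervention, and allowing the detection of statistically significant differences"; two-sided alpha 0.05; power 80%; 1:1 allocation; one baseline and one follow-up. **Assumed:** the pre-post correlation r, which the SAP does not state, and in step 4 the ratio k of follow-up SD to baseline SD.

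**1. The plan's own figure.** n per arm = 2 × (1.960 + 0.842)² × (0.37/0.31)² = 22.36, rounded up to 23. It reproduces, with 0.37 used as the SD of the analysed quantity. If 0.37 is instead the SD at each visit, the SD of change is 0.37 × √(2(1 − r)), which equals 0.37 at r = 0.5.

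**2. Precision with equal SDs.** In units of the visit variance, the change contrast has variance proportional to 2(1 − r) and the adjusted contrast to 1 − r². Their ratio, adjusted to change, is (1 + r)/2. Estimating the slope costs a factor 1 + 1/(N − 4) = 1 + 1/42 = 1.024 at N = 46. The interval ratio is the square root of the variance ratio, times the t quantile on 43 df over that on 44 df (about 1.001). Equivalent n is 23 divided by the variance ratio.

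| r (assumed) | Variance ratio | Half-width ratio | Change interval wider by | 23 adjusted is worth, per arm of change scores |
|---|---|---|---|---|
| 0.3 | 0.67 | 0.82 | 22% | 35 |
| 0.5 | 0.77 | 0.88 | 14% | 30 |
| 0.7 | 0.87 | 0.93 | 7% | 26 |
| 0.9 | 0.97 | 0.99 | 1% | 24 |

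The variance ratio reaches 1 at r = 2/1.024 − 1, about 0.95. At r = 0.5, where both readings of 0.37 agree, the half-width is 0.22 for change and 0.19 Nm/kg adjusted, and noncentral-t power is 79% and 89%.

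**3. Bias.** In 20,000 simulated trials per setting at 23 per arm, with a true difference of 0.31, both estimators averaged between 0.309 and 0.312. Both are unbiased.

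**4. Unequal SDs.** With follow-up SD equal to k times baseline SD, the large-sample ratio, ANCOVA to change, is k²(1 − r²)/(1 + k² − 2rk). At k = 1.25:

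- r = 0.5: 1.172/1.3125 = 0.89.
- r = 0.7: 0.797/0.8125 = 0.98, or 1.00 with the slope cost.
- r = 0.8: 0.5625/0.5625 = 1.00, or 1.02 with the slope cost.

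So the gain can vanish.

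**5. Covariance structure in a common-baseline mixed model.** A random intercept alone forces one variance on both visits. In large samples it weights baseline by p = 2rk/(1 + k²) and reports a variance proportional to (1 + k²)(1 − p²)/2. The true variance of that estimator is k² − 2prk + p², which simplifies to k²(1 − p²). Reported over true variance is therefore (1 + k²)/(2k²), whatever r is:

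- k = 1: 1.00, no problem.
- k = 1.25: 2.5625/3.125 = 0.82. The SE is 0.906 of its true size, and two-sided type I error is 2(1 − Φ(1.96 × 0.906)), about 7.6%.
- k = 1.5: 3.25/4.5 = 0.72. The SE is 0.850 of its true size, and type I error is about 9.6%.

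Simulated null trials at 23 per arm agree: about 5% at k = 1, 6–8% at k = 1.25 and 9–10% at k = 1.5. ANCOVA stayed near 5%. The variance of the random-intercept estimator reached up to 1.28 times that of change scores.

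**The case against.** The strongest reply is that the SAP never prescribes an unadjusted contrast. A model with fixed and random terms could include baseline, so the loss of precision follows from one reading only, and the choice between two unbiased estimators is partly preference. It stands that the documented defect is lack of specification. But the outcome definition, sample size and table shell all point to raw change, and nothing points to adjustment.

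It also stands that adjustment is not always better: the gain depends on r and on the SD ratio, and the SAP gives neither r nor any assurance that the SDs stay equal after training. A common-baseline model with only a random intercept could be worse than the valid contrast it replaces.

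On the non-parametric clause, the reply largely succeeds. Mean differences and intervals are assigned to the mixed model, Table 2 has columns for them, and "The statistical analysis will be performed on allocation codes only". A reader might infer that a switch to ranks would leave nothing to compare with 0.31; the text does not support that. What remains is an open choice with no stated criterion.

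**Conclusion.** The point holds as under-specification with a probable, avoidable loss of precision; it should be corrected. Under the equal SDs that the sample size section assumes, and 23 analysed per arm, the change interval is wider by about 22% at r = 0.3, falling to 1% at r = 0.9 and nothing near 0.95. Those values of r are assumptions.

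Two stronger readings are not supported. One is that the planned analysis is biased or invalid; it is neither. The other is that the trial is underpowered. If 0.37 is the SD at each visit, change-score power would be about 65% at r = 0.3, but also about 95% at r = 0.7, and the SAP does not say which applies. On its own inputs, 23 per group is right.

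**What to change.** In Section 6, Analysis methods, name one primary analysis, either:

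- ANCOVA of 12-week knee-flexor strength on group and baseline strength; or
- a linear mixed model of both visits with time and group-by-time, no group main effect (so a common baseline mean), and an unstructured 2×2 covariance with a separate variance at each visit. This form also yields the within-group changes that Table 2 needs.

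Do not specify a random intercept alone. State that the adjusted 12-week mean difference and its 95% CI are compared with 0.31 Nm/kg, and use the same form for the secondary outcomes.

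As a minor addition, keep this model primary, check its residuals rather than the raw outcomes, and make any rank-based analysis (for example a Wilcoxon rank-sum test on change) a sensitivity analysis.

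The cost is wording plus about one degree of freedom, roughly 2% variance inflation at 23 per arm. No new data are needed. The SAP reports that data collection is unfinished and allocation still concealed, so the choice can be fixed before any result is known.
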